## **Section D: Purpose and Objectives**

Aim. Investigate effects of a meditation intervention designed for Veterans (Inner Resources for Veterans; IRV) on three aspects of rehabilitation in Veterans with both mTBI and PTSD:

Hypothesis 1 (Rehabilitation of Community Integration and Quality of Life): Veterans participating in IRV, relative to an Education Control (EC) group, will exhibit improvements in community reintegration and quality of life after eight weeks of treatment.

Hypothesis 2 (Rehabilitation of Psychological Symptoms): Veterans participating in IRV, relative to an [(EC)] group, will exhibit improvements in PTSD and postconcussive symptoms after eight weeks of treatment.

Hypothesis 3 (Rehabilitation of Neural Networks): Following IRV, functional connectivity in the IRV group will be normalized, e.g., relative to the EC group, Veterans in the IRV group will demonstrate reduced Default Mode Network resting state functional connectivity with lateral prefrontal cortex (LPFC), and increased resting state functional connectivity between the rostral anterior cingulate and amygdala after eight weeks of treatment.

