## Section G: Sample Size/Data Analysis

### G1. Sample Size

How many subjects (or specimens, or charts) will be used in this study?

Local: 60      Worldwide: 60

Please indicate why you chose the sample size proposed:

In a meditation study with Veterans that used mantra repetition, a component of IRV, reductions in Posttraumatic Stress Disorder Checklist total scores showed a moderate-to-large effect size, Cohen's  $d=0.72$  (0.2 is small, 0.5 is moderate, 0.8 is large). A study of loving kindness meditation with Veterans with PTSD reported a large effect size ( $d=0.89$ ) at a three month post-intervention follow-up. A third meditation study also with Veterans from other

war eras with PTSD showed large effect sizes on CAPS in both Intent to Treat (ITT) (Cohen's  $f=0.42$ , approx. equal to  $d=0.84$ ) and completer analyses ( $d=1.24$ ). We more conservatively assume an effect size of  $d=0.63$ . At a significance level of 0.05, with 40 patients (20 patients in each group) we will have power of 0.8 to detect the moderate to large effect size of 0.63. Assuming an attrition rate of 33%, 30 subjects are proposed in each group.

Functional Connectivity MRI Power Analysis (Hyp. 3). In the model that power analysis for fMRI SPM Random Effects Analysis was based on, brain signals are modeled by continuously distributed Gaussian kernels of random height and of width,  $f$ , in proportion to  $W$ , where  $W$  is the smoothness of the random field in units of voxels. Based on the pilot fcMRI data, with effect size of  $d = 0.70$ , observed  $W$  equivalent to [4.9 4.8 4.7] voxels FWHM, observed  $S = 2023$  resels, observed  $f = 2.72*W$ ,  $u = 3.167$ , calculated 2-tailed FWE-corrected cluster  $k_{\alpha}$

$(0.05) = 183$  voxels, shows that a power of 0.82 would be achieved by 20 subjects per group (after attrition). It should be also be noted that cluster sizes greater than this were observed in our fcMRI pilot data.

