Functional Connectivity Processing and Analyses (Hyp 3). The Functional Connectivity Toolbox (Conn) within SPM8 implemented in Matlab (Mathworks Inc. Sherborn MA, USA) will process and analyze the FC data. Images will be realigned, coregistered, normalized in MNI space, and smoothed with a 6 mm FWHM Gaussian filter. Each subject's anatomical image will be segmented into gray and white matter (WM) and cerebrospinal fluid (CSF) masks. Physiological noise and movement will be addressed by using WM and CSF masks and realignment parameters as covariates. Data will be band-pass filtered at .008 - .01 Hz. Artifact Detection Toolbox ([nitrc.org/projects/artifact\\_detect/](http://nitrc.org/projects/artifact_detect/)) will repair artifact due to frame-by-frame head movement, i.e., scrub. WFUPickAtlas will create amygdala regions of interest (ROIs). GLM will estimate correlation between ROIs provided by Conn (e.g., ACC, PCC, MPFC), amygdala, and the whole brain in individual and group random effects analyses. Final T maps of between-groups t-tests will test the contrast, (Post\_IRV ? Post\_EC) MINUS (Pre\_IRV ? Pre\_EC) at the different seed regions. Reported clusters will be statistically significant ( $p=0.05$ , FWE) at the cluster level of inference, using Random Field Theory correction for multiple comparisons.

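### G2 gives the resting-state band-pass as .008 to .01 Hz, only 0.002 Hz wide and probably a typing error; run as written, it would cost Hypothesis 3 most of its precision compared with a wider band

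*Combined protocol and SAP*

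**What the plan says.** The functional connectivity part of G2 (Data Analysis) specifies the filter once: "Data will be band-pass filtered at .008 - .01 Hz". It gives no reason for the band. The estimates follow in the same paragraph: "GLM will estimate correlation between ROIs provided by Conn (e.g., ACC, PCC, MPFC), amygdala, and the whole brain". Noise is handled by regression: "Physiological noise and movement will be addressed by using WM and CSF masks and realignment parameters as covariates". The group comparison of pre-to-post change is then built on those estimates: "Final T maps of between-groups t-tests will test the contrast".

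Section D makes this the only route to Hypothesis 3, under which "functional connectivity in the IRV group will be normalized". G1 (Sample Size) sets the power for that hypothesis "Based on the pilot fcMRI data, with effect size of" d = 0.70, and reports power of 0.82 with 20 per group after attrition. It does not say which filter produced the pilot d. The documents do not give run length, TR or number of volumes.

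**The concern.** A correlation between two filtered series is only as precise as the amount of independent information left in the pass band. A band of 0.002 Hz leaves almost none in a scan of ordinary length. If the software follows the text and the planning effect came from a wider band, each subject's correlation would be so noisy that a real group-by-time change would probably be missed, and a null result could not be interpreted. If the software uses another band, the results are sound but the plan misreports the analysis and leaves the true filter open, so it could be chosen after the data are seen. In either case a reader cannot tell whether the pilot d = 0.70 belongs to the filter in the plan.

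**Working it through.** **Inputs from the documents.** Band 0.008 to 0.01 Hz (G2); d = 0.70, 20 per group, power 0.82 (G1).

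**Assumed, because not stated.** Run length T of 300 to 1200 s; TR of 2 s; comparator upper limits of 0.05 or 0.1 Hz (0.08 Hz also tried); SD of true change between subjects, on the Fisher z scale, up to 0.4.

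**The plan's own figure.** The 0.82 is a cluster-level random-field result. It could not be reproduced, because G1 does not state how d maps to signal height, the field type or the degrees of freedom. A plain two-sided two-sample t-test at 0.05 with d = 0.70 and 20 per group gives 0.578. The 0.82 is neither confirmed nor refuted here, and the point does not rest on it.

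**Step 1: information in the band.** Width = 0.01 − 0.008 = 0.002 Hz. Effective independent samples are about 2 × width × T: 2 × 0.002 × 300 = 1.2, and 2 × 0.002 × 1200 = 4.8. Width × T is 0.6 to 2.4 as written, against 0.042 × T = 12.6 to 50.4 (0.05 Hz) or 0.092 × T = 27.6 to 110.4 (0.1 Hz).

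**Step 2: Fourier frequencies.** A frequency k/T is in the band if 0.008T ≤ k ≤ 0.010T. T = 300 gives k = 3; T = 600 gives k = 5, 6; T = 1200 gives k = 10, 11, 12. At 376 to 398 s there is none, since k = 3 needs T ≤ 375 and k = 4 needs T ≥ 400.

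**Step 3: SD of a null correlation.** For an ideal filter and white noise, SD(r) = 1/√(2m), where m is the number of frequencies in the band.

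| T (s) | m as written | SD(r) | m, 0.05 Hz | SD(r) | m, 0.1 Hz | SD(r) |
|---|---|---|---|---|---|---|
| 300 | 1 | 0.707 | 13 | 0.196 | 28 | 0.134 |
| 600 | 2 | 0.500 | 26 | 0.139 | 56 | 0.094 |
| 1200 | 3 | 0.408 | 51 | 0.099 | 111 | 0.067 |

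With gradual Butterworth filters and white or 1/f spectra, the SD is 0.379 to 0.702 as written, against 0.064 to 0.217 with the wider bands. The ratio is 2.6 to 6.4.

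**Step 4: group contrast.** Variance of the pre-to-post change = (SD of true change)² + 2 × (within-scan SD of z)². The precision retained is the wide-band variance divided by the written-band variance, and the effective d is 0.70 × √(retained). The within-scan SDs of z come from simulated scans with zero true correlation; the comparator upper limit is 0.1 Hz.

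| T (s) | SD true change | SD(z) written / wide | Variance written / wide | Retained | Effective d | Power |
|---|---|---|---|---|---|---|
| 300 | 0.15 | 1.571 / 0.136 | 4.959 / 0.059 | 0.012 | 0.08 | 0.06 |
| 600 | 0.25 | 0.680 / 0.096 | 0.987 / 0.081 | 0.082 | 0.20 | 0.09 |
| 1200 | 0.40 | 0.494 / 0.067 | 0.648 / 0.169 | 0.261 | 0.36 | 0.20 |

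Over all settings of this calculation (upper limit 0.08 or 0.1 Hz), 73% to 99% of group-level precision is lost. Separate simulations with a baseline z of 0.3, a between-subject SD of 0.2, true-change SD of 0 to 0.4 and an upper limit of 0.05 or 0.1 Hz gave an effective d of 0.09 to 0.42 and power of 0.056 to 0.259.

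**Not evaluated.** Scrubbing, the nuisance covariates and cluster-level inference. If the covariates are fitted to the filtered data, WM, CSF and an assumed six realignment terms already make eight, more than the 1.2 to 4.8 effective samples.

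**The case against.** The strongest reply is that this is an evident slip with no likely consequence. If the software is set to a wider band, the results stand and only the text needs correcting. The loss of power needs two things that nobody has verified: that the software runs the written band, and that the pilot used a wider one. If the pilot used the written band, d = 0.70 already includes the loss. That is right, and the size of the harm is conditional on both.

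Other objections also carry weight. The comparison from 58% to 6–26% is for one uncorrected t-test and must not be read against the planned 0.82. The upper end depends on capping the SD of true change at 0.4; at 0.6 and 1200 s, d would be about 0.46 and power about 0.30. The counts of 1, 2 and 3 each include a frequency exactly at 0.01 Hz and become 0, 1 and 2 without it, and the gap at 376 to 398 s holds only for an ideal filter on an unpadded series. The contrast in the same paragraph of G2 has lost its operators in the converted text, so the digit should be checked in the source PDF.

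None of this makes the written band usable. Even at an SD of 0.6 and 1200 s, 56% of group-level precision is lost against a 0.1 Hz limit. The filter is a working parameter of the analysis, and the documents offer no other value to fall back on.

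**Conclusion.** The concern holds. The filter as written would lose most of the precision of the Hypothesis 3 estimates relative to a conventional-width comparison band: 73% to 99% at group level for a true-change SD of 0.15 to 0.4, assumed runs of 5 to 20 minutes and an assumed upper limit of 0.08 or 0.1 Hz. The fall in d and power applies only if the pilot d = 0.70 came from a wider band. A typing error is the likeliest explanation, but the documents do not establish the intended limit. One of the three hypotheses is at stake; the CAPS primary outcome is not. This should be fixed before analysis, and it is not fatal to the trial.

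**What to change.** Before analysis, check three things: the figure in the source PDF, the band set in the analysis software, and the band used in the pilot pipeline. Correct the upper cut-off in G2 to the intended value (0.1 Hz if that was meant), and say that the same band applies to pre- and post-treatment scans. Beside it, state the TR, the run length and the filter behind d = 0.70. If the pilot and the plan both really use 0.008 to 0.01 Hz, say so and justify it. The cost is one number and three descriptive items, with no change to data collection.

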## G2. Data Analysis

Provide a description of your plan for data analysis. State the types of comparisons you plan (e.g. comparison of means, comparison of proportions, regressions, analysis of variance). Which is the PRIMARY comparison/analysis? How will the analyses proposed relate to the primary purposes of your study?

All analyses will be done on an intention-to-treat basis, indicating that all randomized participants and all outcomes will be included in the analysis according to their assigned treatment groups regardless of their adherence to their assigned treatment or their purported relationship to the treatment. Baseline Analysis: Imbalance in groups may occur by chance; we will examine baseline characteristics (e.g., age and psychotropic medication) of participants randomized to the two groups. Chi-square and t-tests will be used to evaluate the differences between groups for categorical and continuous variables, respectively.

Behavioral Outcome Analyses (Hypotheses 1-2). For all outcomes, we will examine the normality of the

distribution of the variable to determine if transformations such as log or inverse might be needed. In order to control for type I error due to multiple comparisons on multiple tests, we will use a rank sum scoring approach. There will be one rank sum score variable for the CAPS (primary outcome measure), and one for psychological tests (secondary outcome measures). The primary analysis is to assess the meditation effect, for which we will use a general linear mixed model, containing terms of treatment, time period, and interaction between time and treatment. The treatment effect will measure differences between the intervention and control groups at baseline, and the time effect will measure whether there was an overall change over time in the outcome. The term of most interest will be the interaction between time and treatment. A secondary analysis will include covariates of age and medication usage Method for Missing data: Because a research assistant verifies completion of each item, missing data are anticipated to be low. We assume any missing data will be missing at random, which can be indirectly verified by comparing the distribution of other important measures between patients with and without complete data. We will apply multiple imputation methods on the missing data and impute the missing data 20 times.

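### Hypothesis 3 is tested on several whole-brain seed maps with Random Field Theory holding 5% only within each map, no correction across seeds, and no dedicated test that decides the hypothesis

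*Combined protocol and SAP*

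**What the plan says.** Section D introduces Hypothesis 3 broadly: "functional connectivity in the IRV group will be normalized, e.g., relative to the EC group". It then gives two directional examples. One is lower connectivity of the Default Mode Network with lateral prefrontal cortex. The other is "increased resting state functional connectivity between the rostral anterior cingulate and amygdala after eight weeks of treatment".

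The analysis in G2 (Functional Connectivity Processing and Analyses) is wider. It states that "GLM will estimate correlation between ROIs provided by Conn (e.g., ACC, PCC, MPFC), amygdala, and the whole brain", so the seed list is itself introduced by an e.g. and the target is every voxel. The group-by-time contrast is tested on T maps "at the different seed regions". Clusters are reported at p = 0.05, FWE, at cluster level, "using Random Field Theory correction for multiple comparisons".

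No sentence in G2 fixes the number of seeds, ranks them or adjusts across them. The other multiplicity device in G2, the rank sum score, belongs to the behavioral outcomes of Hypotheses 1 and 2. The imaging power analysis in G1 gives one cluster threshold (183 voxels) and one power (0.82 with 20 per group), and mentions no number of seeds.

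**The concern.** Random Field Theory accounts for searching many voxels within one statistical map. It does not account for producing several maps and reporting whichever clusters pass in any of them. With four named seeds and room for more, the chance of a false corrected cluster somewhere in the Hypothesis 3 analysis is higher than the 5% a reader would attach to the FWE label.

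The second issue is what counts as success. G2 does not mention LPFC, does not specify the rostral part of the ACC, and sets no target region or mask for either example connection. The seed maps could show both connections, but nothing says which result, in which map, would confirm or refute Hypothesis 3. A cluster elsewhere, from a listed or added seed, would carry the same corrected label as one in the hypothesised location.

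**Working it through.** **Inputs from the documents.** Level 0.05 FWE per cluster map (G2). Four named seeds: ACC, PCC, MPFC, amygdala (G2). Imaging power inputs (G1): d = 0.70, 20 per group after attrition, S = 2023 resels, W = 4.9 × 4.8 × 4.7 voxels FWHM, u = 3.167, two-tailed k = 183 voxels, power 0.82.

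**Assumptions.** Each map is tested at 0.05, which is the ordinary reading of a plan silent on seeds. The correlation between maps is not given, so a range is shown.

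**1. The plan's own figure.** For one map, 1 − (1 − 0.05)^1 = 0.05. The stated level is reproduced for a single seed.

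**2. Several seeds.** With m independent maps the family-wise error is 1 − 0.95^m. The Bonferroni bound, valid under any dependence, is 0.05m.

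| Seeds m | Independent | Bound |
|---|---|---|
| 2 | 9.75% | 10% |
| 3 | 14.3% | 15% |
| 4 (those named) | 18.5% | 20% |

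**3. Correlated seeds.** PCC and MPFC belong to the same network, so independence is unlikely. Take one Gaussian score per map, equal correlation between the four maps, and each score cut at its upper 5% point:

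| Assumed correlation | Family-wise error, 4 seeds |
|---|---|
| 0.3 | 16.4% |
| 0.5 | 14.5% |
| 0.7 | 12.0% |
| 0.9 | 8.8% |

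The rate falls to 5% only if the maps are effectively identical.

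**4. Does k = 183 already contain a seed correction?** Use P(largest cluster ≥ k) = 1 − exp(−E·exp(−b·k^(2/3))), with the expected cluster count E and the constant b derived from S, W and u. For one map at 0.025 per tail this gives k = 145 for a Gaussian field and 173 for a t field with 38 df (5.5% below 183). It gives 184 to 182 for 26 to 28 df, which the document does not state. A Gaussian high-threshold form at 0.00625 per tail, which would be a four-seed correction, gives 180. The threshold therefore does not settle the question, and no text claims such a correction.

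**5. Level needed.** Four seeds at 5% overall: 0.05/4 = 0.0125 per map. Two named connections: Holm starts at 0.05/2 = 0.025.

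**6. Power of a single connectivity test.** Assume the G1 effect size carries over to a two-group t-test with 20 per group. The noncentrality is 0.70 × √(20/2) = 2.214 on 38 df. At two-sided 0.05 the critical value is 2.024 and power is 0.58. At 0.025 it is 2.334 and power is 0.46.

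**7. Power of corrected seed maps (illustration only).** Scale 183 by the ratio of t-field thresholds (38 df) at 0.00625 and 0.025 per tail: 183 × 227.3/172.9 ≈ 241 voxels. In the random-signal model that G1 describes, with the signal set to return 0.82 at 183 voxels, power falls to about 0.62.

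**The case against.** The strongest reply is that several harsher readings fail, and they do.

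- A reader might infer that the plan breaks a stated 5% guarantee. G2 attaches 0.05 to clusters within a map, where it is nominally held, and never promises 5% across seeds.
- A reader might infer that the two connections go untested. PCC and MPFC maps cover connectivity with LPFC, and ACC and amygdala maps cover rostral ACC-amygdala. What is absent is a dedicated, deciding test.
- A reader might treat the two connections as the whole hypothesis. Section D introduces them with e.g., so a finding elsewhere is not strictly outside its wording.
- A reader might blame the whole-brain search for the inflation. Random Field Theory already corrects for that; only the number of maps inflates error.
- A reader might quote 23%. That needs five independent seeds, for example a left-right amygdala split, which G2 does not specify.
- A reader might infer an intention-to-treat breach. G2 states "All analyses will be done on an intention-to-treat basis", and a post-minus-pre map needs both scans, but nothing says participants with one scan are dropped. The imputation text sits in the behavioral paragraph, so imaging is simply not addressed.

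It is also fair that F1 declares a pilot and that G2 makes CAPS the primary outcome, so no primary conclusion depends on this analysis.

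What remains is an open seed list, no correction across maps, and no deciding test for one of three formal hypotheses that has its own power analysis. The loose wording of the hypothesis makes a fixed test more necessary.

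**Conclusion.** The point holds in this form. Across the four named seeds the chance of at least one false corrected cluster is about 9% to 16% at assumed correlations of 0.9 to 0.3, 18.5% under independence, and no more than 20%. It grows if seeds are added. These figures rest on testing each map at 0.05 and on correlations that the documents do not supply. Separately, Hypothesis 3 has no pre-set criterion for being met. The consequence is moderate: it limits what can be claimed about neural networks and leaves the CAPS result untouched. The change should be made before the imaging data are analysed.

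**What to change.** Before analysis, add to G2:

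- **Two confirmatory values.** One DMN-LPFC value, averaged over listed DMN nodes and both LPFC sides, and one rostral ACC-amygdala value, averaged over sides. The averaging rule must be written down; otherwise the choice of nodes and sides brings multiplicity back.
- **One test for each.** The treatment-by-time interaction, with Holm across the two, in the mixed model already planned for the behavioral outcomes. This keeps participants with one scan, although a baseline-only participant adds little to the interaction.
- **Everything else.** Label the remaining whole-brain clusters exploratory, or close the seed list and test each map at 0.05 divided by the number of seeds (0.0125 for four).

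The cost is SAP wording and a small extraction of connectivity values; no data collection changes. Clusters outside the named connections lose confirmatory status. The G1 imaging power (0.82 at k = 183) is for cluster inference on one map and must be restated. If d = 0.70 is assumed for a single connectivity test with 20 per group, power is about 0.58 at two-sided 0.05 and 0.46 at Holm's first step. Dividing alpha over four maps also costs power, to roughly 0.62 in the illustration above.

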## **Section F: Design/Procedure**

### **F1. Design**

Select one category that most adequately describes your research:

c) Pilot

Discuss the research design including but not limited to such issues as: probability of group assignment, potential for subject to be randomized to placebo group, use of control subjects, etc.

This is a prospective, randomized, controlled, single-blinded intervention study. Subjects will be randomized to either the IRV Meditation group or the Education Control group and have a 50% chance of being in either group.

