#### Pre- and post-treatment fMRI Scans

Before beginning and approximately 12 weeks after completing the IRV intervention or EC groups, participants will be invited to participate in an MRI scan. Study staff will review safety issues related to MRI with the subject and answer any questions. The MRI scanner we will use is a conventional 3.0 Tesla scanner that has been approved for clinical use by the FDA. A mental health provider or trained study staff with experience working with psychiatric populations will be present in the scanner control room throughout the experiment for immediate availability if the patient becomes agitated or frightened. In an effort to reduce the possibility that subjects will be adversely affected by the scanner noise or the appearance of visual stimuli, subjects may be acclimated to the scanner by being permitted to enter it prior to the scan to become familiar with the sounds and enclosed space of the scanner. These habituation procedures have been very successful in terms of stress and movement reduction. Veterans will be informed that if they do not complete the entire scan, they will still be compensated. Should the participant indicate at any time that they choose to discontinue the study, the study will be terminated at no penalty to the subject. Subjects who potentially have metal in their bodies but are not sure, e.g., subjects with a history of welding, will be asked to undergo x-ray in order to identify whether there is metal in their bodies. A radiologist will be asked to review the MRI scans of the subjects and provide reports of his review as a courtesy to the subjects.

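### Hypothesis 3 is tested on raw pre-to-post change in connectivity; adjusting the post scan for the pre scan would be more precise from the same data, by an amount the documents do not fix

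*Combined protocol and SAP*

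**What the plan says.** Section G2 (Functional Connectivity Processing and Analyses, Hyp 3) states that "Final T maps of between-groups t-tests will test the contrast" formed by the post-treatment IRV/EC difference minus the pre-treatment IRV/EC difference, at each seed region. I read the character between the arms within each bracket as a minus sign. The result is mean change in IRV minus mean change in EC.

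The only covariates named for this analysis deal with noise: "Physiological noise and movement will be addressed by using WM and CSF masks and realignment parameters as covariates". The adjusted analysis described earlier in G2 ("A secondary analysis will include covariates of age and medication usage") belongs to the behavioural outcomes of Hypotheses 1 and 2. Nowhere is post-treatment connectivity adjusted for pre-treatment connectivity.

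Both scans are planned. Section F2 says: "Before beginning and approximately 12 weeks after completing the IRV intervention or EC groups, participants will be invited to participate in an MRI scan". Section F1 says that subjects "have a 50% chance of being in either group". The imaging power statement in G1 takes d = 0.70 from pilot data and a two-tailed family-wise cluster threshold, and gives power 0.82 with 20 per group after attrition. It reports no pre-post correlation and does not say whether d is in units of the SD of change or of a single scan.

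**The concern.** A change score subtracts the whole of the pre scan, noise included. That weight is best only when the regression slope of post on pre is 1. When the slope is smaller, the contrast carries variance that a regression on the pre value would remove. If r is below 0.5, with equal variances, the change score is even noisier than comparing the post scans alone.

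Precision is scarce here. The plan expects to go from 30 randomised to 20 evaluable per group. Anyone who contributes an observed change score already has both scans, so adjustment needs no new data. The imaging analysis is also separate from the behavioural mixed model and has its own power statement, so a change in how the behavioural model handles baseline would not reach it.

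**Working it through.** **Inputs from the documents.** 20 evaluable per group, d = 0.70, two-tailed 0.05, cluster-forming threshold u = 3.167, critical cluster 183 voxels, stated power 0.82 (all G1); 1:1 allocation (F1).

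**Assumptions.** r is not given, so I take 0.3 to 0.9, with equal pre and post variance s². The scale of d is not given, so both readings are shown.

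**The plan's own figure.** A random-field cluster model with u taken as a t on 38 df (z = 2.964) and 0.025 per tail gives a critical cluster of 181 voxels against the stated 183. Its power with signal SD 0.70 is 0.77 against the stated 0.82; about 0.73 would be needed for 0.82. Since G1 does not say how d and n enter the model, this does not show 0.82 to be wrong. Nothing below uses it.

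**Variance per subject.**
- Change score: 2s²(1−r).
- Post adjusted for pre: s²(1−r²).
- Ratio: (1−r²)/(2(1−r)) = (1+r)/2.
- Estimating one slope with N = 40 multiplies the adjusted variance by 1 + 1/36 = 37/36.
- Break-even: (37/36)(1+r)/2 = 1 gives r = 2(36/37) − 1 = 0.946.

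**Power at one location, d in change-SD units.** The change-score noncentrality is 0.70 × √(20/2) = 2.214 on 38 df, which gives power 0.58. For the adjusted test it is 2.214 divided by the square root of the variance ratio, on 37 df. Equivalent n is 20 divided by the ratio. The interval narrows by 1 − √ratio.

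| r | (37/36)(1+r)/2 | Noncentrality | Adjusted power | Equivalent n per group as change | Interval narrower by |
|---|---|---|---|---|---|
| 0.3 | 0.668 | 2.708 | 0.75 | 29.9 | 18% |
| 0.5 | 0.771 | 2.521 | 0.69 | 25.9 | 12% |
| 0.8 | 0.925 | 2.302 | 0.61 | 21.6 | 4% |
| 0.9 | 0.976 | 2.240 | 0.59 | 20.5 | 1% |

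Simulation (20,000 runs per value of r) agrees: about 0.58 for change, and 0.755, 0.688 and 0.595 adjusted at r = 0.3, 0.5 and 0.9.

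**Power at one location, d in single-scan SD units.** The change-scale effect is then 0.70/√(2(1−r)).

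| r | Change | Adjusted |
|---|---|---|
| 0.3 | 0.45 | 0.61 |
| 0.5 | 0.58 | 0.69 |
| 0.7 | 0.80 | 0.85 |
| 0.8 | 0.93 | 0.94 |

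**Which covariate.** The gain requires each location to be adjusted for its own pre value. Suppose instead that one summary value per subject is used and correlates 0.3 with post at a given voxel (assumed). The variance relative to the change score is (1−0.3²)/(2(1−r)): 0.91/0.6 = 1.52 at r = 0.7 and 0.91/0.4 = 2.28 at r = 0.8. That is a loss.

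**The case against.** The strongest reply is that nothing is broken. The contrast is valid under randomisation, the study is classed as a pilot, CAPS is the primary outcome, and the contrast parallels the time-by-treatment interaction used for the behavioural outcomes. All of that stands. A reader might infer that the change-score test is biased or inflates type I error; the randomised design rules that out. A reader might also count chance baseline imbalance, acting through regression to the mean, as a second harm. It is the same excess variance already in the ratio above.

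The second reply is that the size is unknown. This also stands. The documents give no r, it will differ by seed and voxel, and at r = 0.9 the gain is about one power point. The scans are roughly 20 weeks apart (8 weeks of sessions plus about 12) and H1 allows either of two facilities. Both could lower r, but that is inference.

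The third reply is that 0.58 is not this plan's power. That is correct. A reader might set 0.58 against the statement that "a power of 0.82 would be achieved by 20 subjects per group (after attrition") and conclude that G1 overstates power. The documents do not support this: G1 refers to a cluster-level random-field test and the figures here to a single location, and one does not convert exactly into the other.

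**Conclusion.** The point holds as an efficiency recommendation. The plan tests raw change where a baseline-adjusted comparison of the same scans targets the same effect with smaller variance for any r below about 0.946, given equal variances and 40 participants. The gain is substantial for r of 0.5 or less (11 to 17 power points at one location with d on the change-SD scale), modest at 0.8 (about 3 points) and negligible at 0.9. If d is on the single-scan scale, the gain is similar at low r but only about 5 points at r = 0.7 and 1 to 2 points at r = 0.8. The direction is secure. The size depends on an r and an effect-size scale that the documents do not state.

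**What to change.** Pre-specify in G2 that, for each named connection (for example rostral anterior cingulate to amygdala), post-treatment Fisher-z connectivity is regressed on arm and on the same subject's pre-treatment value for that connection, with the arm term as the test.

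For the seed-to-whole-brain maps, use the same model with the pre-treatment value at the same voxel and from the same seed as the covariate, and exclude a single summary value per subject. If voxel-wise covariates cannot be implemented, keep the change contrast for the maps and adjust only the region-of-interest tests. Keep the change contrast as a sensitivity analysis throughout. In G1, report the pilot pre-post correlation and state the scale of d = 0.70.

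The cost is SAP wording, one degree of freedom, a different second-level design and some scripting for the voxel-wise covariate. No extra scans are needed. If r proves to be about 0.9 or higher, almost nothing is gained; above about 0.946 there is a very small loss.
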